Appendix 8. Performance Status According to Eastern Cooperative Oncology Group (ECOG) 11.8

	ECOG Performance Status Scale
Grade	Descriptions
0	Fully active, able to carry on all pre-disease performance without restriction
1	Restricted in physically strenuous activity but ambulatory and able to carry out work of a light or sedentary nature, eg, light house work, office work
2	Ambulatory and capable of all selfcare but unable to carry out any work activities. Up and about more than 50% of waking hours
3	Capable of only limited selfcare, confined to bed or chair more than 50% of waking hours
4	Completely disabled. Cannot carry on any selfcare. Totally confined to bed or chair
5	Dead

ECOG = Eastern Cooperative Oncology Group. Source: Oken et al, 1982

Protocol Number: 20200439

Date: 05 June 2024 Page 158 of 176

11.9 Appendix 9. Modified Response Evaluation Criteria in Solid Tumors Version 1.1 (Modified RECIST 1.1)

Response Evaluation Criteria in Solid Tumors version 1.1 (RECIST 1.1) are guidelines for assessing tumor burden changes in response to treatment (Eisenhauer et al, 2009). Additional patterns of response have been observed with immune-enhancing therapies, including delayed clinical response, leading to criteria modifications to capture treatment responses more accurately (Nishino et al, 2013; Wolchok et al, 2009). This study utilizes modified RECIST 1.1 criteria which applies aspects of the immune-related response criteria (including requiring confirmation of disease progression) to RECIST 1.1 as outlined below.

Modified RECIST 1.1 tumor response assessment

 All measurable and non-measurable lesions should be assessed at screening, all defined tumor assessment time points (Schedule of Assessment), and any unscheduled imaging visits.

Measurable lesions:

- Non-nodal lesions with clear borders that can be measured accurately and serially in one dimension in the axial plane (longest diameter ≥ 10 mm measured by magnetic resonance imaging/computed tomography [MRI/CT] with scan slice thickness ≤ 5 mm).
- Nodal lesions with the longest diameter perpendicular to the long axis (short axis)
 ≥ 15 mm on MRI/CT.
- Must exclude simple cysts, pleural/pericardial effusions and ascites.

Non-measurable lesions:

- All other lesions, including small lesions (longest diameter < 10 mm or pathological lymph nodes with ≥ 10 mm but < 15 mm short axis) are considered non-measurable and characterized as non-index lesions.

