Response assessment: index lesions (calculated from % chan in tumor burden)	ge	 CR: Disappearance of all lesions Pathologic lymph nodes short axis < 10 mm PR: ≥ 30% decrease from baseline SD: Does not meet criteria for CR, PR or progressive disease. Progressive disease: ≥ 20% increase (and ≥ 5 mm absolute increase) from nadir 											
Response assessment: non-index lesions		 CR: Disappearance of all lesions Pathologic lymph nodes short axis < 10 mm SD: Persistence of one or more non-index lesion(s) Progressive disease: Unequivocal progression of existing non-index lesions 											
New Lesions		The presence of new lesion(s) defines progression											
Confirmation		Confirmation by su required for CR, P	•	essment after ≥4 weeks ssive disease.									
Summary of N	Modi	fied RECIST 1.1 Ov	erall Respons	e Assessment									
Index lesions (tumor burden) ^a , %	No	n-Index lesions	New lesions	Overall Response using modified RECIST 1.1									
↓ 100%	Ab	sent	Absent	CR ^b									
Noned	Ab	sent	Absent	CR⁵									
↓ 100%	Pre	esent	Absent	PR^b									
↓≥30 %	Ab	sent/Present	Absent	PR^{b}									
↓ < 30% to ↑ < 20%	Ab	sent/Present	Absent	SD									
Noned	Pre	esent	Absent	SD									
↑≥ 20%	An	У	Any	Progressive disease ^c									
Any		equivocal gression	Any	Progressive disease ^c									
Any	An	y	Present	Progressive disease ^c									
NA/ND/UE	Ab	sent/Present	Absent	UE									
Noned	NA	/ND/UE	ND/UE Absent										

CR = complete response; NA = not available; ND = not done; PR = partial response; RECIST = Response Evaluation Criteria in Solid Tumors; **SD = stable disease;** UE = unable to evaluate

^a Decrease assessed relative to baseline. Increase assessed relative to nadir.

^b Response: CR and PR require a confirmation assessment after ≥ 4 weeks, may also wait until the next scheduled imaging

^c Progression: Progressive disease requires a confirmation assessment

^d Subjects with non-index lesions only

Protocol Number: 20200439

Date: 05 June 2024 Page 162 of 176

11.10 Appendix 10. Schedule of Activities:

Table 11-4. List of Schedule of Activities Tables

Quick link to Schedule of Activities	Table Title
Table 11-5	One-Step Dosing – Cycle 1 only (AMG 404 Administered
Table 11-6	One-Step Dosing – Cycle 1 only (AMG 404 Administered
Table 11-7	One-Step Dosing – Cycle 1 only (AMG 404 Administered
Table 11-8	Cycle 2 and Beyond (AMG 404 Administered on in Cycle 1)
Table 11-9	Cycle 2 and Beyond (AMG 404 Administered on in Cycle 1)

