For parameters/assessments not scheduled to be performed (or scheduled but not performed) on the same day as the earliest date of first administration of tarlatamab or AMG 404 the baseline value is the value from the screening period measured closest to the day earliest date of first administration of tarlatamab or AMG 404. In the event that multiple assessments are done on the same day as the earliest date of first administration of tarlatamab or AMG 404 and there is no time associated with the assessments, the value associated with the last clinically planned event before the earliest date of first administration of tarlatamab or AMG 404 will be used as the baseline value.

Baseline ECG

Baseline ECG is the Cycle 1 pre-dose assessment. If Cycle 1 pre-dose assessment is missing, the last non-missing assessment(s) taken prior to the first administration of tarlatamab or AMG 404 treatment will be used as the baseline ECG.

Date: 27 Sep 2024 Page 22 of 51

Best Overall Response (BOR)

Best overall response (BOR) for a subject is the best observed post baseline disease response per modified response evaluation criteria in solid tumors (modified RECIST 1.1). Overall response assessments occurring after the start of the first subsequent anticancer therapy will not be included.

BOR is defined as the best response in the following order: CR, PR, SD, PD, or NE, where CR, PR and PD require confirmation by a repeat, consecutive scan at least 4 weeks after the first documentation of response. A best overall response of SD requires an on-study imaging of SD or better no earlier than days after cycle 1 otherwise the best overall response will be not evaluable (NE).

Please refer the Appendix B for more details.

Body Mass Index (BMI)

Body Mass Index should be calculated using the following formula

BMI
$$(kg/m^2)$$
 = weight (kg) / [height $(cm)/100$]²

Body Surface Area (BSA)

The Body Surface Area should be calculated using the following formula

BSA=
$$0.007184 \times weight(kg)^{0.425} \times height(cm)^{0.725}$$

Change from Baseline

Change from Baseline is the arithmetic difference between post-dose assessments and Baseline.

Change (absolute) from Baseline = (Post-baseline Value – Baseline Value)

C_{max}

Maximum observed serum concentration of tarlatamab.

C_{min}

Minimum observed serum concentration of tarlatamab.

Disease control rate (DCR)

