Percent change from baseline is the arithmetic difference between post-baseline and baseline divided by baseline values times 100.

Change (percent) from Baseline = [(Post-baseline Value – Baseline Value) /

Baseline Value] x 100

Date: 27 Sep 2024 Page 27 of 51

Progression-free survival (PFS) per Modified RECIST 1.1

PFS (in Months) per modified RECIST 1.1 is defined as the interval from the earlier date of first dose of Tarlatamab or AMG 404 to the earlier of PD per modified RECIST 1.1 or death due to any cause.

The censoring rules for the progression-free survival analysis are detailed in Appendix C.

Relative Dose Intensity

Relative dose intensity is calculated as actual cumulative dose / planned cumulative dose.

- Actual cumulative dose [mg] is defined as the total dose given during the study treatment exposure up to the study visit. For subjects who did not take any drug the actual cumulative dose is 0 mg.
- Planned cumulative dose [mg] is defined as the per-protocol planned dose accumulated over the actual duration on study treatment, whether the actual visit is missing or not.

Safety Follow-Up (SFU)

The first SFU visit is defined as the subject visit up to after last dose of tarlatamab or AMG 404, whichever occurs later, or prior to initiation of other anti-cancer therapy, whichever occurs first. The second SFU visit is defined as the subject visit up to after the end of the last dose of AMG 404 or prior to initiation of other anti-cancer therapy, whichever occurs first.

Study Day 1

It is defined as the first day that tarlatamab or AMG 404 is administered to the subject.

Time to Response (TTR)

TTR is defined as the time from the earlier date of first dose of tarlatamab or AMG 404 to the date of the first documented CR or PR that is subsequently confirmed per Modified RECIST1.1. TTR will be calculated only for confirmed responders.

Treatment-Emergent Adverse Event (TEAE)

Date: 27 Sep 2024 Page 28 of 51

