Appendix B. BOR Calculation Algorithm

Confirmed BOR by Investigator

At each time point, BOR will be derived based upon the evaluated time points up to and including the current assessment. The following rules will apply to BOR:

- CR is better than PR is better than SD is better than PD is better than NE
- For a BOR of SD, a duration of ≥ since the cycle 1 is required
- For a BOR of CR, PR or PD, confirmation is required in a consecutive assessment ≥ after the initially observed assessment of CR, PR or PD except the following cases
 - An unlimited number of intermittent assessments of NE or CR can occur between the initial response and the confirmation of CR. For example, BL, CR, NE, NE, NE, CR the CR at post-baseline 1 is confirmed at post-baseline 5. SD is not allowed between CR and subsequent confirmation CR.
 - An unlimited number of intermittent assessments of NE, SD, PR or CR < can occur between the initial response and the confirmation of PR. For example, BL, PR, SD, SD, SD, PR – the PR at post-baseline 1 is confirmed by post-baseline 5.
 - An unlimited number of intermittent assessments of NE can occur between the initial PD and the confirmation. (No reference though)
 - PD doesn't need confirmation if PD is the last evaluable assessment PD and determines BOR or PD time of PFS.

Table 8 provides the BOR determination per modified RECIST 1.1 for trials where confirmation for response and progressive disease are required. A BOR determined by Table 8 is considered a Confirmed_BOR. Table 9 outlines the steps to derive Confirmed_BOR (step 1) given investigator's time point assessments.

Interim BOR by Investigator

At interim futility analyses, due to lack of sufficient follow-up time for confirmation san, study team may choose to report both confirmed responders and unconfirmed responders (subjects had an initial PR or CR and still has potential for future confirmative scans). Interim BOR is defined to include unconfirmed responders in addition to those who achieve Confirmed BOR. Table 9 step 2 is the step to derive these unconfirmed responders.

Confirmed and Interim BOR by Central Review

Date: 27 Sep 2024 Page 47 of 51

Confirmed and Interim BOR by Central Review will be derived from Time point response by Central. The steps are same as derivation for Confirmed and Interim BOR by Investigator (Table 8 and Table 9)

Protocol Number: 20200439

Date: 27 Sep 2024 Page 48 of 51

Product: AMG 757, AMG 404

Table 8. BOR per Modified RECIST 1.1

		1	1			

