Appendix C. PFS Calculation and Censoring Rule

Table 10 defines PFS censoring rule per modified RECIST 1.1 PD from radiographic scans.

Table 10. PFS Censoring Rule

Situation up to DCO/EOS	Date of Event or Censor	Outcome
No evaluable post-baseline tumor assessments, no death recorded	Date of Randomization date (or first dose date of IP in non- randomized trials)	Censor
PD	Date of first detection of PD	Event
No PD, but death recorded	Date of death	Event
Start of new anti-cancer therapy prior to any PD or death	Date of last evaluable tumor assessment before or on start of new anti-cancer therapy	Censor
	Date of last evaluable tumor assessment	Censor
more missed tumor assessment (18	Date of last evaluable tumor assessment prior to missing assessment(s) ^a	Censor

Note: PD's does not require confirmation if based on RECIST 1.1.

DCO = Data Cutoff; EOS = End of Study; PD = Progressive disease ^a This supersedes the previous rules that result in PFS event at date of PD or death.

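### The PD row of SAP Table 10 has no confirmation condition, which conflicts with Protocol 11.9 and SAP Appendix B and, read literally, can give a confirmed responder a negative duration of response

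*SAP*

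**What the plan says.** SAP Section 5 defines PFS as running to "the earlier of PD per modified RECIST 1.1 or death due to any cause". Appendix C opens in the same terms: "Table 10 defines PFS censoring rule per modified RECIST 1.1 PD from radiographic scans". In Table 10 itself, the PD row gives "Date of first detection of PD" as the event date and counts it as an event, without mentioning confirmation. The only note on the subject reads "PD's does not require confirmation if based on RECIST 1.1".

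Elsewhere, confirmation is part of the criterion:

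- Protocol 11.9 describes its changes to RECIST 1.1 as "including requiring confirmation of disease progression", and a footnote to its summary table repeats that "Progressive disease requires a confirmation assessment".
- The best overall response (BOR) definition in SAP Section 5 lists response categories "where CR, PR and PD require confirmation by a repeat, consecutive scan at least 4 weeks after the first documentation of response".
- SAP Appendix B has one exception, and it names PFS: "PD doesn't need confirmation if PD is the last evaluable assessment PD and determines BOR or PD time of PFS".

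In SAP Section 5, DOR and duration of disease control (DoDC) both end at progression or death and both refer to Appendix C for censoring. SAP Section 10 declares no changes from the protocol-specified analyses.

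**The concern.** The modified criteria were adopted because immune-enhancing treatment can produce a delayed response, so a first PD reading may not be the real end of benefit. An event rule that takes any first PD removes that protection from PFS, DOR and DoDC in the very subjects it was meant for.

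Such scan sequences are expected under this plan. Treatment may run to confirmed progression (Protocol 1.2), and imaging after discontinuation for other reasons continues until confirmed PD (Protocol 8.1.4). SAP Table 8 rows C29 and C30 provide for PD followed by response or stable disease. SAP Table 9 takes the best response over visits, and only assessments after new anticancer therapy are left out of BOR. A subject can therefore be a confirmed responder for BOR and, under a literal Table 10, have progressed before the response began. Two programmers could follow this SAP in good faith and report different PFS and DOR for that subject.

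**Working it through.** The plan prints no figure on this point, so there is none to reproduce. The check takes illustrative scan sequences through the SAP's own rules.

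**Inputs**

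- Scan interval of 8 weeks: notes to SAP Table 8 (X = 8). Assumed: scans fall exactly on schedule and days are counted from first dose, so weeks 8, 16, 24 and 32 are days 56, 112, 168 and 224.
- Confirmation at least 4 weeks later: SAP Section 5, BOR.
- DOR in months = (progression or death date - response start + 1) x 12 / 365.25: SAP Section 5.
- Response start: first evidence of response in SAP Section 5; the confirmation scan in Protocol 11.9.
- PFS in months is taken as days x 12 / 365.25, since the SAP prints no PFS formula.

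**Sequence A: PD week 8, PR week 16, PR week 24**

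1. BOR. At week 16, Table 8 row C29 (PD, then CR, PR or SD beyond the 7-week minimum, X - 1) gives SD. At week 24, Table 9 step 1 pairs the PR with the PR 8 weeks earlier and gives PR. The best over visits is PR.
2. PFS under literal Table 10. Event at day 56: 56 x 12 / 365.25 = 1.84 months.
3. DOR under literal Table 10, from first evidence: (56 - 112 + 1) x 12 / 365.25 = -55 x 12 / 365.25 = -1.81 months. From the confirmation scan: (56 - 168 + 1) x 12 / 365.25 = -3.65 months.

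An earlier repeat scan does not prevent this. With PD at week 8 and PR at weeks 12 (day 84) and 16, DOR from first evidence is (56 - 84 + 1) x 12 / 365.25 = -0.89 months.

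**Sequence A continued: PD again at weeks 32 and 40**

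| Quantity | Literal Table 10 (day 56) | Confirmation required (day 224) |
|---|---|---|
| PFS | 1.84 months | 224 x 12 / 365.25 = 7.36 months |
| DOR from first evidence | -1.81 months | (224 - 112 + 1) x 12 / 365.25 = 3.71 months |
| DOR from confirmation scan | -3.65 months | (224 - 168 + 1) x 12 / 365.25 = 1.87 months |

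The right-hand column still dates the confirmed PD at its first scan, week 32.

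**Sequence B: PD week 8, PD week 12, PR week 16, PR week 24**

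This PD is confirmed, and Protocol 7.2 allows treatment to continue under conditions. BOR does not stop at PD, so it is again PR. The PD date is day 56 under either reading of Table 10, and DOR from first evidence is -1.81 months both times. Correcting the PD row alone does not remove this case.

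**The case against.** The strongest defence is that the note is conditional. It speaks of RECIST 1.1, while the lead sentence of Appendix C and the PFS definition both say modified RECIST 1.1. On that reading it waives nothing in this trial and is probably template text, since the same table also provides for a randomization date in a trial that has no randomization. Confirmation would then come from the PFS definition and Appendix B, and the negative DOR would appear only if Table 10 were read in isolation.

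Much of this stands. A reader might infer that the SAP waives confirmation outright, but the note's wording does not support that. A reader might also infer that dating PD at first detection contradicts modified RECIST. It does not: the entry sits in the date column, a confirmed PD can properly be dated at its first scan, and Protocol 11.9 gives a dating rule for CR and PR but none for PD. Nor does the last-scan exception come from the protocol; it is in the SAP only.

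The defence does not make the table consistent. If the note is irrelevant, what remains is an event row with no confirmation condition in the table that governs the analysis. If the note is meant to apply, it contradicts Protocol 11.9. In neither case does Table 10 state the Appendix B rule, whose exception would be pointless if PFS never required confirmation. Table 10 cannot be defended as a deliberate departure either, since Section 10 declares none.

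**Conclusion.** The point holds as a conflict between rules. Table 10 as printed does not agree with Protocol 11.9 or with SAP Appendix B, and following it literally gives wrong PFS, DOR and DoDC dates for any subject whose unconfirmed PD is followed by a non-PD scan. In the worked sequence PFS is 1.84 instead of 7.36 months, and DOR is -1.81 instead of 3.71 months. These values assume exact 8-week scans, a 4-week confirmation interval and response dated at first evidence.

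The number of subjects affected is unknown. The documents give no rate of unconfirmed PD, and enrolled numbers are blacked out. A negative DOR also needs a later confirmed response, so it concerns only part of that group and possibly nobody. A reader might infer that requiring confirmation in Table 10 cures every negative DOR; sequence B shows that it does not.

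The endpoints are secondary and descriptive and no hypothesis is tested, so this should be corrected before the final analysis but does not threaten the trial's primary safety objective.

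**What to change.** 1. In Table 10, reword the PD row to: PD confirmed at a consecutive assessment at least 4 weeks later, or PD at the last evaluable assessment (Appendix B); event dated at first detection of that PD. An unconfirmed PD followed by a non-PD assessment is then not an event.
2. Delete the note about RECIST 1.1.
3. State that the same progression rule applies to DOR and DoDC.
4. State that responses first seen after confirmed PD do not count toward BOR or DOR. This closes sequence B.
5. Choose one start for DOR, reconciling first evidence of response (SAP Section 5) with the confirmation scan (Protocol 11.9).
6. Record in SAP Section 10 that the last-evaluable-assessment exception is the SAP's own, since Protocol 11.9 does not contain it.

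The cost is a few lines in the SAP and the matching derivation code. No new data are needed.
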